### 5.2.3 Toxicity Grading

The NCI CTCAE version 5.0 will be used for grading the severity of AEs and modifications to the dosing of venetoclax and DEC-C will be made according to this severity grading. If more than 1 type of toxicity occurs concurrently, the most severe grade will determine the modification. For purpose of any necessary definition, “baseline value” is defined as the most immediately known value in place prior to patient’s first receipt of protocol-indicated treatment on Cycle 1, Day 1.

#### Severity criteria (NCI/CTCAE):

The term “severe” is used to describe the intensity of an AE; the event itself could be of relatively minor clinical significance (e.g., ‘severe’ headache). This is not the same as “serious.” Seriousness of AEs is based on the outcome of an AE and usually associated with events that pose a threat to a patient’s life or functioning.

The severity of the AE will be graded according to the NCI/CTCAE Grading Scale (see the CTCAE web page at <http://ctep.cancer.gov> for details). For AEs not covered by CTCAE, the severity will be characterized as “mild,” “moderate,” or “severe” according to the following definitions:

- Mild events are usually transient and do not interfere with the patient’s daily activities.
- Moderate events introduce a low level of inconvenience or concern to the patient and may interfere with daily activities.
- Severe events interrupt the patient’s usual daily activities.

### 5.2.4 Dose-Limiting Toxicity

A dose-limiting toxicity (DLT) is defined as any toxicity that occurs up to day 28 during the dose de-escalation (pre-remission) phase and is at least possibly related to study drug administration. This does not include toxicity with a clear alternative explanation (e.g., disease progression) or transient ( $\leq 72$  hours) abnormal laboratory values without

associated clinically significant signs or symptoms based on investigator determination. All DLTs will be assessed by the investigator using CTCAE v5.0 criteria.

To be considered evaluable, subjects must fulfill the following minimum criteria:

- All doses of DEC-C.
- 75% of doses of venetoclax during the first cycle (e.g., 21/28 or 16/21 days)

All patients who initiate venetoclax/DEC-C, receive at least one dose of each, and experience a DLT are evaluable regardless of whether the minimum criteria above are met.

Subjects experiencing toxicity that results in dose-holds will remain evaluable provided the minimum criteria outlined above are met. Patients that require dose reductions during the DLT evaluation period (e.g., first 28 days after initiation of the first dose of study treatment/C1D1) will not be considered a DLT so long as they receive the minimum doses at the prescribed dose level outlined above.

Patients who achieve a morphologic remission on C1D22 BMBx, have not experienced a DLT, and have treatment interrupted due to favorable treatment response will be considered evaluable if they complete 75% of protocol-directed doses (i.e., a patient who achieves a remission and is instructed to stop venetoclax on C1D24 is considered evaluable provided they received at least 18/24 venetoclax doses, or 75%) and will not be replaced.

Patients missing >25% of venetoclax doses, or any DEC-C doses due to adverse event(s), will be considered a DLT provided the AEs are considered related. If unrelated, the patient may be replaced as described above.

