**Notes:**

[figure not shown]
1. Informed consent must be obtained before any screening assessments are performed. Screening assessments are to be performed within 14 days prior to Day 1 of Cycle 1 unless otherwise noted. Assessments performed as standard of care within the screening window may be used for screening. Baseline characteristics include but are not limited to demographics, medical and surgical history, extent of disease, prior anti-cancer treatment.
2. Vital Signs to include: Blood pressure (BP), heart rate (HR) and temperature. To be done at least once on days indicated and thereafter, ideally prior to any receipt of study drug. Any additional recordings per local site's standard of care/ treating physician discretion.
3. Review and capture of all concomitant medications will be performed as indicated. Concomitant medications include prescription medications and over-the-counter preparations used by a patient within at least 14 days prior to first dose of protocol-defined treatment and continuing through at least the 28-day Follow-Up study visit. After signing informed consent, adverse events will be collected and followed at least until 28 days after a patient's final protocol-directed treatment with DEC-C/venetoclax (whichever occurs last) or until initiation of another anti-cancer therapy – whichever occurs first.
4. Surveillance for toxicity related to DEC-C/venetoclax to establish RP2D. For patients enrolled in the dose exploration (or dose de-escalation) part of the study, dedicated surveillance including satisfactory assessment of the physical exam and safety labs is required to help detect evidence of past or present DLT as having occurred during the first 28 days of protocol-indicated treatment. Expedited reporting of Dose Limiting Toxicity (DLT) required as outlined in [Section 5.2.4](#). See [Section 5.2.4](#) for definition of DLT and toxicities which, if experienced during the first 28 days after initiating protocol-indicated treatment, shall be considered dose limiting.
5. Hematology includes white blood cell count with differential, hemoglobin, hematocrit, and platelet count. Blood Chemistry to include sodium, potassium, chloride, bicarbonate or carbon dioxide, blood urea nitrogen (BUN), creatinine, glucose, total bilirubin, AST, ALT, alkaline phosphatase, calcium, albumin, and total protein.

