**Pre-remission phase:**

Dose Level 1:      DEC-C 100mg/35mg on days 1-5  
                         Venetoclax 400mg/day x 28 days

Dose Level -1:      DEC-C 100mg/35mg on days 1-4  
                         Venetoclax 400mg/day x 28 days

Dose Level -2:      DEC-C 100mg/35mg on days 1-4  
                         Venetoclax 400mg/day x 21/28 days

Three initial patients will be enrolled at dose level 1 during the pre-remission phase of treatment. If there are 0 dose limiting toxicities (DLTs), then enrollment will proceed at this dose level. If there is 1 DLT, then 3 additional subjects will be enrolled. If  $\geq 2$  DLTs in six patients, dose level -1 will be evaluated using a similar approach, followed by dose level -2. See [Table 4](#).

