**Table 4: Dose De-escalation Rules**

Number of Patients with Drug-Related DLT at a Given Dose Level	Dose De-escalation Step
0 of 3	Proceed as RP2D
1 of 3	Treat 3 more patients at the same dose level
$\geq 2$ of 3	Enrollment at this dose level stops. Proceed to next lower dose level
$\leq 1$ of 6	Proceed as RP2D
$\geq 2$ of 6	Proceed to next lower dose level

All patients will be considered evaluable for DLT unless they cannot complete the first cycle of therapy due to withdrawal of consent or disease progression. A patient who is not DLT-evaluable will be replaced. Cohort review discussions will be held between the study chair and other investigator(s) to confirm dose escalation, reductions, and cohort expansions.

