#### Definition of Dose-Limiting Toxicity – Hematologic:

- Neutropenia: Progression/development of grade 4 neutropenia and bone marrow aplasia without evidence of disease that extends >2 weeks beyond the end of a treatment cycle.
- Thrombocytopenia: Progression/development of grade 4 thrombocytopenia and bone marrow aplasia without evidence of disease that extends >2 weeks beyond the end of a treatment cycle.

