#### Exceptions

Adverse events that meet the above definitions but that are clearly unrelated to study drug will not be DLTs.

In rare instances, an event may fall within the definition of a DLT, as defined above, but the event may be considered not to be a DLT (e.g., not be clinically meaningful). If this occurs, the study chair and other investigator(s) will review the event and supporting data. The reasons for not considering the event to be a DLT will be clearly documented with supporting rationale.

Patients who have experienced a DLT do not automatically require discontinuation of protocol-indicated treatment, unless the nature or severity of the DLT is also an adverse event that would require permanent discontinuation of study treatment as elsewhere defined by the protocol (e.g. [Section 5.2.4](#)). Rather, a patient who has experienced a DLT should be evaluated for consideration of an appropriate dose hold or dose modification which, if consistent with the protocol, would allow continued dosing under revised circumstance.

**A dose limiting toxicity (DLT) must be reported by the site using expedited notification procedures.** Within 1 business day of investigator awareness of an adverse event meeting DLT criteria, the event must be reported to the sponsor-investigator by both of the following two mechanisms:

- 1) recorded in the electronic case report form (eCRF) and
- 2) separate email alert to [[contact]](mailto:[contact])

If a DLT meets seriousness criteria, such event must also be reported as an SAE (see protocol [Section 6.2](#) and [Section 6.3](#)).

For the purpose of ensuring an appropriate opportunity to determine the recommended phase 2 dose (RP2D) of venetoclax/DEC-C, a subject who is withdrawn from the study prior to completing the DLT assessment window (e.g. first 28 days after initiating

protocol-indicated treatment on Cycle 1, Day 1) for reasons other than a DLT will be considered not evaluable for DLT and will be replaced.

Additionally, over the first 28 days after initiating study therapy, if a patient discontinues study treatment for reasons clearly not related to protocol-indicated treatment (in the judgement of the study chair and other investigator(s)) and fails to complete the minimum number of doses of venetoclax/DEC-C, then that patient may be considered not evaluable for response and be replaced with a new patient.

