**Table 5: Venetoclax/DEC-C Dose Level Summary (Pre-remission Phase)**

DOSE LEVEL	VENETOCLAX	DEC-C
1	400mg once daily Continuous Day 1-28 Δ	100mg/35mg once daily Days 1-5
-1	400mg once daily Continuous Day 1-28 Δ	100mg/35mg once daily Days 1-4
-2	400mg once daily Continuous Day 1-21 Δ	100mg/35mg once daily Days 1-4

\* Cycles are every 28 days.

Δ Venetoclax dosing will be ramped on C1D1 and C1D2 per [Figure 3](#).

During the pre-remission phase, it is intended that venetoclax will be dosed continuously per the dose level summary ([Table 5](#)) and will not be interrupted unless the day C1D22 BMBx is negative for leukemia. Missed days of venetoclax due to treatment interruption in a patient with aplastic marrow that is negative for AML, who are otherwise tolerating therapy well and without evidence of a DLT, will not influence evaluability (i.e., required minimum number of venetoclax doses).

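### The DLT window closes on day 28, but the hematologic DLT cannot be met before day 43, and no written rule marks a patient with unresolved aplasia as pending

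*Combined protocol and SAP*

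**What the plan says.** Three places set a 28-day limit.

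- Section 5.2.4, general definition: "A dose-limiting toxicity (DLT) is defined as any toxicity that occurs up to day 28 during the dose de-escalation (pre-remission) phase".
- Schedule of Activities, Note 4: surveillance looks for "evidence of past or present DLT as having occurred during the first 28 days of protocol-indicated treatment".
- Section 5.2.4, Exceptions: a patient withdrawn "prior to completing the DLT assessment window (e.g. first 28 days after initiating" treatment on C1D1 for reasons other than a DLT is replaced.

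The hematologic definition in the same section has one clause for neutropenia and one for thrombocytopenia. Each requires grade 4 cytopenia and "bone marrow aplasia without evidence of disease that extends >2 weeks beyond the end of a treatment cycle". Section 5.2.2 sets the cycle at 28 days.

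The decision rules do not mention this longer horizon. Section 5.2.2 says "If there are 0 dose limiting toxicities (DLTs), then enrollment will proceed at this dose level". In Table 4, one DLT in three leads to "Treat 3 more patients at the same dose level", two or more in three stops enrollment at the level, at most one in six makes it the RP2D, and two or more in six moves to the next lower level. The text under Table 4 makes patients evaluable once they complete the first cycle. The text under Table 5 adds that "Missed days of venetoclax due to treatment interruption in a patient with aplastic marrow that is negative for AML" will not affect evaluability, provided the patient otherwise tolerates therapy and has no DLT. Table 10 uses the Section 5.2.4 definition through Section 9.3.1.

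**The concern.** Prolonged disease-free aplasia is the only toxicity in the hematologic DLT definition, and that definition cannot be satisfied inside the window the same section sets. Sites could apply either of two readings.

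- **Literal.** Only events met by day 28 count, so the hematologic clause has no effect in Table 4 or Table 10.
- **Onset.** Aplasia starting by day 28 counts once confirmed. This is likelier, because the clause refers to progression or development, a D42 marrow is planned, and DLT checks continue after cycle 1. But the patient's status is then unknown from day 28 to day 43, and nothing says how to score the patient meanwhile.

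At stake is whether a dose level is expanded or declared the RP2D before the outcome is known in a patient with unresolved aplasia.

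**Working it through.** **Dates.** Cycle 1 ends on day 28. Two weeks later is day 42, so more than two weeks is first met on day 43, and 43 − 28 = 15 days after the window closes. If the reference is a second pre-remission cycle, the date is 56 + 14 + 1 = day 71. The D42 marrow falls exactly two weeks after day 28, so alone it cannot show the criterion is met.

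**The plan's own figures.** Table 10 follows from a Beta(1,1) prior and posterior P(DLT rate > 0.20) > 0.80. For 2 of 6 the posterior is Beta(3,5), giving 0.852. The eight boundaries give 0.852, 0.839, 0.836, 0.804, 0.811, 0.818, 0.825 and 0.854. All reproduce. Only the definition of what is counted is in question.

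**How many patients are open.** Call a patient open if DLT-free at day 28 and not yet at day 43. Assume even accrual of 34 to 51 patients over the planned 24 months. Spacing is 24 × 30.44 / 34 = 21.5 days, or 24 × 30.44 / 51 = 14.3 days. When patient 3 reaches day 28, patient 2 is at about day 49 or day 42, and patient 1 at day 71 or day 57. Usually one patient is open; at the faster pace two can be.

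**Assumed rates.** The documents give no rate of prolonged aplasia. Take an aplasia DLT rate h of 10%, 20% or 30% and other DLTs at 10%, independent. The 30% value is high, since only patients whose marrow clears can qualify and the design's target response rate is 35%.

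**Chance that a later event changes the count.** With k open patients this is 1 − (1−h)^k: 10%, 20%, 30% for k = 1 and 19%, 36%, 51% for k = 2. The consequence depends on the count:

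- 1 of 3 becomes at least 2 of 3, where enrollment at the level should stop.
- 1 of 6 becomes at least 2 of 6, where the next lower level is due.
- 0 of 3 with one open becomes at most 1 of 3, and enrollment continues at the same level either way. With two open it becomes 2 of 3 with probability h² = 1%, 4% or 9%.

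**Chance that Table 4 clears a level.** Let p = 1 − 0.9(1−h) = 0.19, 0.28 or 0.37.

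- With a pending rule: (1−p)³ + 3p(1−p)⁵.
- Without one, last patient of each cohort open: 0.9(1−p)² + 2p(0.9)(1−p)⁴ + (0.1)(0.9)(1−p)⁴.
- Literal reading, aplasia never counted: 0.9³ + 3(0.1)(0.9⁵) = 0.906.

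| h | With pending rule | Without, one open | Rise | Literal |
|---|---|---|---|---|
| 10% | 0.730 | 0.776 | 0.046 | 0.906 |
| 20% | 0.536 | 0.626 | 0.090 | 0.906 |
| 30% | 0.360 | 0.476 | 0.116 | 0.906 |

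The rise has two parts. The 0 of 3 route, 0.9h(1−p)²[1 − (1−p)³], gives 2.8, 5.8 and 8.0 points. The 1 of 6 route, 0.9h(2p + 0.1)(1−p)⁴, gives 1.9, 3.2 and 3.6 points. Every extra clearance has at least two DLTs in the first six patients, which is the first Table 10 boundary. The 1 of 3 case does not enter the rise, because patient 3's outcome is known when six patients are read. Its cost is up to three more patients treated at a level Table 4 would have stopped.

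**The case against.** The strongest reply is that only the onset reading gives every section effect. A literal reading would void the hematologic definition and leave little purpose for the DLT surveillance at post-remission Cycle 1 Day 1 and Cycle 2 Day 1 (Sections 7.5.1 and 7.6.1). This stands as the likelier intent, but no sentence says so, and Note 4 still ties the event to the first 28 days.

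A reader might infer that hematologic toxicity is never counted. The documents do not support that. Under Section 5.2.4, missing more than 25% of venetoclax doses or any DEC-C dose because of a related adverse event is a DLT, and Section 5.2.6.1 interrupts both drugs for neutropenic fever. What the literal reading loses is prolonged aplasia.

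A reader might also infer that a late event would go unseen. That is too strong. Post-remission Cycle 1 Day 1 follows ANC recovery in aplastic patients, when the length of the neutropenia is known, and Section 5.2.6.3 schedules further marrows for persistent cases. These find the event but do not set when the cohort decision is taken. Pre-remission Cycle 2 helps little, since it is for patients whose C1D22 marrow is still involved.

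Finally, a reader might infer that a required de-escalation is lost. Nothing makes the Table 4 decision irrevocable: "Cohort review discussions will be held between the study chair and other investigator(s) to confirm dose escalation, reductions, and cohort expansions", and under Section 5.2.5 the study chair determines de-escalation and the RP2D. If late events count, Table 10 pauses at 2 of 6. These are real safeguards, but the cohort review has no stated timing, and whether late events count is the point left undefined.

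**Conclusion.** Wrong as written, and should be fixed. The contradiction is certain and needs no outside data: a 28-day window cannot contain an event first met on day 43, and no text creates a pending status or ties the later checks to Tables 4 and 10.

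The practical effect depends on the reading. Taken literally, the prolonged-aplasia clause has no effect in either table. On the likelier onset reading the effect is modest: a rise of about 5 to 12 points in the chance that Table 4 clears a level. That rests on the assumed 10% to 30% aplasia rates, 10% other DLTs, independence, even accrual, and a decision taken at the last patient's day 28 without revisiting. More than half of the rise comes from the 0 of 3 route, where the next patients would largely enroll at the same level anyway.

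**What to change.** 1. Define the hematologic DLT as grade 4 neutropenia or thrombocytopenia with disease-free aplasia that starts by day 28 of cycle 1 and persists past day 42. Confirm it with the planned D42 marrow and a routine CBC just after day 42.
2. Say explicitly whether aplasia after a second pre-remission cycle counts, since the present wording is not limited to cycle 1.
3. Score a patient with unresolved grade 4 cytopenia and aplasia at day 28 as pending, not DLT-free, in Tables 4 and 10.
4. Do not declare the RP2D while a patient is pending. Hold the next Table 4 step only when the pending result could change it, for example 1 of 3 or 1 of 6 with one or more pending, or 0 of 3 with two or more pending. With 0 of 3 and one pending, enrollment at the same level can continue.

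The cost is protocol wording, one routine blood count, and an occasional wait of about two weeks.

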#### Definition of Dose-Limiting Toxicity – Non-hematologic

- Grade 3 nausea, vomiting, dehydration, diarrhea, or fatigue lasting > 3 days despite optimal supportive medications. Patients who require tube feeds or total parenteral nutrition will be considered a DLT.
- Any other Grade 3 non-hematological toxicity with the following exceptions:
  - Grade 3 or 4 electrolyte abnormalities that:
    - Improve with supportive care to  $\leq$  Grade 2 within 72 hours
    - Are deemed not medically significant (i.e. hospitalization not indicated or non-life-threatening) by the investigator.
  - Hair loss
  - Grade 3 AST, ALT, or alkaline phosphatase elevations that last <72 hours
- Any other Grade 4 non-hematologic toxicity.
- Patients meeting criteria for Hy's Law as follows:
  - Aminotransferase elevations, often much greater than 3x ULN, with elevation in serum total bilirubin to >2xULN without initial findings of cholestasis (elevated serum alkaline phosphatase).
  - No other reason is identified to explain the combination of increased aminotransferase and total bilirubin, such as viral hepatitis, pre-existing

- acute liver disease, or another drug capable of causing the observed injury.
- Any grade 5 non-hematologic toxicity will be considered a DLT.

#### Definition of Dose-Limiting Toxicity – Hematologic:

- Neutropenia: Progression/development of grade 4 neutropenia and bone marrow aplasia without evidence of disease that extends >2 weeks beyond the end of a treatment cycle.
- Thrombocytopenia: Progression/development of grade 4 thrombocytopenia and bone marrow aplasia without evidence of disease that extends >2 weeks beyond the end of a treatment cycle.

#### Exceptions

Adverse events that meet the above definitions but that are clearly unrelated to study drug will not be DLTs.

In rare instances, an event may fall within the definition of a DLT, as defined above, but the event may be considered not to be a DLT (e.g., not be clinically meaningful). If this occurs, the study chair and other investigator(s) will review the event and supporting data. The reasons for not considering the event to be a DLT will be clearly documented with supporting rationale.

Patients who have experienced a DLT do not automatically require discontinuation of protocol-indicated treatment, unless the nature or severity of the DLT is also an adverse event that would require permanent discontinuation of study treatment as elsewhere defined by the protocol (e.g. [Section 5.2.4](#)). Rather, a patient who has experienced a DLT should be evaluated for consideration of an appropriate dose hold or dose modification which, if consistent with the protocol, would allow continued dosing under revised circumstance.

**A dose limiting toxicity (DLT) must be reported by the site using expedited notification procedures.** Within 1 business day of investigator awareness of an adverse event meeting DLT criteria, the event must be reported to the sponsor-investigator by both of the following two mechanisms:

- 1) recorded in the electronic case report form (eCRF) and
- 2) separate email alert to [[contact]](mailto:[contact])

If a DLT meets seriousness criteria, such event must also be reported as an SAE (see protocol [Section 6.2](#) and [Section 6.3](#)).

For the purpose of ensuring an appropriate opportunity to determine the recommended phase 2 dose (RP2D) of venetoclax/DEC-C, a subject who is withdrawn from the study prior to completing the DLT assessment window (e.g. first 28 days after initiating

protocol-indicated treatment on Cycle 1, Day 1) for reasons other than a DLT will be considered not evaluable for DLT and will be replaced.

Additionally, over the first 28 days after initiating study therapy, if a patient discontinues study treatment for reasons clearly not related to protocol-indicated treatment (in the judgement of the study chair and other investigator(s)) and fails to complete the minimum number of doses of venetoclax/DEC-C, then that patient may be considered not evaluable for response and be replaced with a new patient.

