11. During the first three days of therapy, tumor lysis syndrome (TLS) precautions will include scheduled outpatient visits with TLS laboratory studies. Therapy with a uric acid reducing agent (e.g., allopurinol initiated at least 2-3 days prior to the start of therapy) is required. Laboratory monitoring for TLS (per institution standard of care) will occur prior to the first dose on cycle 1 day 1 and continue for the first three days of cycle 1. Unless contraindicated, allopurinol must be continued through the end of cycle 1. Intravenous fluids should be administered daily during the ramp-up period. Patients with clinical evidence of TLS should be hospitalized.
12. The study will provide decitabine/cedazuridine (DEC-C) to the sites. Treatment with DEC-C will begin on Cycle 1 Day 1 after receiving anti-TLS hydration/prophylaxis. It is intended that patients will receive DEC-C until progression of disease, unacceptable toxicity, revocation of consent, or for up to 12 months of post-remission therapy. DEC-C is to be taken without food at the same time each day. See [Section 5.2.1.2](#).
13. Sites will obtain commercial (standard of care) venetoclax. Venetoclax will begin on Cycle 1 Day 1 after receiving anti-TLS hydration/prophylaxis. Venetoclax dosing is ramped to 400mg/day. It is intended that patients will receive venetoclax until progression of disease, unacceptable toxicity, revocation of consent, or for up to 12 months of maintenance. Venetoclax is taken with food at the same time each day. See [Section 5.2.1.1](#).
14. On Cycle 1, Day 1 only: Physical exam; ECOG performance status; and weight will be obtained unless performed within the prior 7 days. Confirmation of a negative pregnancy test is required in all women of childbearing potential prior to beginning protocol-directed therapies.
15. All patients will undergo bone marrow aspiration and biopsy on cycle 1 day 22 to assess treatment response and for correlative studies. Patients with at least a partial response (PR) to treatment who receive a second cycle of full-intensity therapy will have repeat biopsy at cycle 2 day 22. Aspirate and matching PD blood samples will be sent for correlative studies.

16. Beginning in the post-remission phase: To accommodate scheduling, Day 1 and 15 visits/procedures may occur with flexibility of  $\pm$  3 days.

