17. Reasonable effort should be made to complete End-of-Treatment (EOT) procedures on the day it is decided a patient will no longer receive protocol-indicated treatment. These procedures must be completed subsequent to and not later than 10 days after investigator decision to permanently discontinue protocol-indicated treatment with DEC-C or venetoclax (whichever treatment occurs last) and prior to any subsequent anti-cancer therapy.
18. At End-of-Treatment: If patient discontinues study treatment for reason other than progressive disease confirmed by biopsy procedure (e.g. due to adverse event), then every effort should be made to obtain fresh biopsy samples to evaluate response and to obtain biospecimens including matching PD blood samples for exploratory research. If progressive disease is suspected between scheduled study biopsies (e.g. due to peripheral blood counts), then fresh biopsy and PD blood samples must be collected in a subsequent procedure to evaluate for progressive disease and to obtain bio specimens for research purposes; if progressive disease is confirmed in that procedure and the patient will terminate the study as a result, then these procedures may be used as the end of treatment procedures.
19. Follow-up clinic visit to be completed within 28 to 35 days after patient's final protocol-indicated treatment with DEC-C or venetoclax (whichever occurs last). Documented attempt(s) must be made for patient return to the study clinic. It will not be considered a protocol deviation if the patient is physically unable to return for the follow-up visit; such circumstance should be recorded in the study documents, and as much of the follow-up information as possible should be obtained from local and outside facilities. Note: The study may continue to request results of laboratory data conducted outside of the study but related to peripheral blood counts or bone marrow biopsy, until progressive disease is ultimately confirmed.
20. Each patient will be followed for survival every 3 months ( $\pm$  14 days) after patient's final protocol treatment with DEC-C or venetoclax (whichever occurs last) until death, end of the study, until patient withdraws consent, or for a maximum of 2 years after the patient's final protocol-indicated treatment – whichever comes first. Survival contact can be made via clinic visit, chart review, obituary or similar observation (e.g. Social Security death index), or by telephone.

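### Section 5.2.4 lets a treated patient who stops early be ruled not evaluable for response and replaced, and Section 9 defines no response set to prevent it

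*Combined protocol and SAP*

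**What the plan says.** The rule is the last sentence of Section 5.2.4, Exceptions. It applies over the first 28 days "if a patient discontinues study treatment for reasons clearly not related to protocol-indicated treatment", as judged by the study chair and other investigators, when the minimum doses are also missed. In that case, "then that patient may be considered not evaluable for response and be replaced with a new patient". Section 5.2.4 sets the minimum as every DEC-C dose plus "75% of doses of venetoclax during the first cycle", for example 21 of 28.

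DLT replacement has its own text:

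- The sentence just before says that a patient withdrawn during the DLT window "for reasons other than a DLT will be considered not evaluable for DLT and will be replaced".
- Below Table 4 (Section 5.2.2): "A patient who is not DLT-evaluable will be replaced".
- Section 5.2.4, on doses missed because of adverse events: "If unrelated, the patient may be replaced as described above".

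On response, Section 9.2 names the IWG criteria. Section 9.3 and the Synopsis give the two-stage rule, with stage 1 counted in enrolled patients and the final stage simply as 34 patients. Both add a 15% (n=5) drop-out allowance on top of the 34. Section 9 defines no response analysis set and does not say how a treated patient without a response assessment is counted.

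**The concern.** The primary endpoint is an investigator-assessed composite CR rate in an open-label, single-arm trial. A rule that lets the study team decide, after treatment has begun, which patients leave the denominator puts that rate at risk. The rule is discretionary, is not confined to the dose-finding cohort, and does not exclude early progression or leukemia-related death. Section 5.2.4 itself gives disease progression as an example of a clear alternative explanation to drug toxicity, so an early progressor could be judged to have stopped for an unrelated reason.

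The timing makes upward bias plausible. Note 15 to the schedule of activities sets the first response marrow: "All patients will undergo bone marrow aspiration and biopsy on cycle 1 day 22 to assess treatment response". Replacing patients who stopped before it, instead of counting them as non-responders, could raise both the reported rate and the chance of wrongly rejecting 15%.

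**Working it through.** **The plan's own figures.** Take a null rate of 15%, a target of 35%, 80% power and alpha 0.05 (one-sided, since the null is a rate at or below 15%). An exact search for Simon's optimal design gives 9 patients in stage 1, continue with at least 2 responders, 34 in total, reject with at least 9. Type I error is 4.7%, power 81.1%, early termination 59.9% and expected size 19.0. The plan's 34, 60% and 19 therefore reproduce, but with a first stage of 9. The written first stage is 20 patients, continuing with at least 3 responders. That mismatch, and the two different final cut-offs (at least 9 in the Synopsis, more than 9 in Section 9.3), are separate matters. The written rule is used below with both cut-offs.

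**Timing.** With no missed days, a patient on 28-day venetoclax with fewer than 21 doses took the last one by day 20, before the day 22 marrow. Note 18 asks for an end-of-treatment marrow after early stopping ("every effort should be made to obtain fresh biopsy samples to evaluate response"), so some of these patients will be assessed.

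**Type I error with replacement.** Let k patients be replaced on top of 34 retained, and let those replaced respond at rate q.

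- Share replaced: f = k / (34 + k).
- If the rate in all treated patients is 15%, the rate among those retained is p = (0.15 − q·f) / (1 − f).
- P(reject) = Σ over x = 3 to 20 of P(X₁ = x) · P(X₂ ≥ r − x), where X₁ ~ Bin(20, p), X₂ ~ Bin(14, p), and r = 9 or 10.

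Example: k = 5 and q = 0 give f = 5/39 = 0.128 and p = 0.15 / 0.872 = 0.172.

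The documents do not give k. The range 1 to 5 is an assumption, and 5 equals the whole drop-out allowance (0.15 × 34 = 5.1).

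| Response rate of those replaced (q) | k | At least 9 of 34 | More than 9 of 34 |
|---|---|---|---|
| any | 0 | 5.8% | 2.4% |
| 0% | 1 | 6.8% | 2.9% |
| 0% | 3 | 9.0% | 4.0% |
| 0% | 5 | 11.6% | 5.5% |
| 5% | 1 | 6.4% | 2.7% |
| 5% | 5 | 9.4% | 4.3% |
| 10% | 1 | 6.1% | 2.5% |
| 10% | 5 | 7.5% | 3.2% |
| 15% | 1 to 5 | 5.8% | 2.4% |

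**Effect on one result.** If five non-responders had been replaced, a reported 10/34 = 29.4% would be 10/39 = 25.6% of all treated patients. The single-stage exact one-sided p-values against 15% are 0.024 and 0.058. This shows how much the denominator matters; the analysis proposed below would use the first 34 treated, not all 39.

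**Power cost of counting all treated patients.** If 35% was meant for evaluable patients only, the all-treated rate is 0.35 × 34/35 = 34.0% with one replaced non-responder, and 0.35 × 34/39 = 30.5% with five.

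| All-treated rate | Power, at least 9 | Power, more than 9 |
|---|---|---|
| 35% | 88.9% | 80.4% |
| 34.0% | 86.5% | 76.8% |
| 30.5% | 75.0% | 61.8% |

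**The case against.** The strongest reply is that this is one wrong word. The sentence closes the DLT exceptions, follows a sentence whose stated purpose is to determine the RP2D, covers the same 28 days and uses the DLT dosing test. Read as *DLT* it is not even redundant: the sentence before covers withdrawal from the study, while this one covers stopping treatment. That reading may well be the intended one. It still needs a one-word correction, because the text says *response* and carries no limit to the dose-finding patients.

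Second, stage 1 is counted in enrolled patients, which would keep early stoppers in. That is a partial safeguard: it conflicts with Section 5.2.4 and does not extend to the final 34. The drop-out allowance on top of 34 fits a denominator that leaves drop-outs out.

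Third, the direction is not certain. A patient who missed one DEC-C dose, had the day 22 marrow and then discontinued for an unrelated reason would also meet the rule, and could be a responder. Note 18 also requires a fresh marrow when progression is suspected between scheduled biopsies. These points narrow the likely bias without removing it.

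Fourth, 11.6% is an extreme. It needs five replacements, no responders among them and the lower cut-off, and 5.8 points of it are the baseline. One replacement adds at most 1.0 point (at least 9) or 0.5 point (more than 9). With the 9-patient first stage that reproduces the plan's 60% and 19, the range for one to five non-responders is 5.5% to 9.6% (at least 9), and no value exceeds 4.8% with the higher cut-off. All of this stands as a limit on size.

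**Conclusion.** The concern holds. As written, the plan permits discretionary removal of treated patients from the primary response rate, and Section 9 does not override it. The bias would be upward if the replaced patients respond less often than the rest, and absent if their stopping is unrelated to response.

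The size is conditional on an assumed 1 to 5 replacements, and the full range needs none of them to respond. With the higher cut-off, only the extreme case (five replaced, no responders) takes type I error above 5%. If the sentence is read as covering only the dose-finding cohorts, five replacements are unlikely. Confidence is medium, because *DLT* may have been meant. The correction should be made under either reading.

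**What to change.** 1. In Section 5.2.4, Exceptions, delete the sentence or change *response* to *DLT*, so that replacement serves DLT evaluability only.
2. In Section 9, define the primary response set as the first 20 patients (stage 1) and first 34 (final), in order of enrolment, who receive at least one dose of study drug. Count anyone without a documented CR/CRh/CRi, for whatever reason, as a non-responder. State that replacement for DLT purposes does not remove a patient from this set.
3. Report the evaluable-only rate as a sensitivity analysis.

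Two further clarifications would help. Reconcile the 15% (n=5) drop-out allowance with this set, for example by limiting it to DLT replacement and to patients registered but never dosed, whose registration Section 6.1 cancels. State separately whether dose-finding patients treated at the RP2D count toward the 20 and 34; this point does not settle that.

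The change is to protocol and SAP wording only, but it has a statistical price. The reported rate may be slightly lower. If 35% was meant for evaluable patients, power falls as tabulated above: under the higher cut-off, one replaced non-responder already takes it below the stated 80%.
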